### **6.10.3. Additional Analyses of the Primary Outcome**

There will be no adjustment for multiple comparisons for additional analyses beyond the aforementioned primary and major secondary analyses in Sections 6.10.1 and 6.10.2.

In the additional analyses of primary outcome of ASAS40, treatment groups of ixekizumab 80 mg Q2W and Q4W will be analyzed without regard to starting dose, unless indicated otherwise.

To support the primary outcome analysis, ASAS40 will be analyzed based on the PPS Populations for Period 2 at Week 16 (Visit 8) [using PPS-16] and Week 52 (Visit 15) [using PPS-52] using a logistic regression analysis with treatment, geographic region, and screening MRI/CRP status in the model (Section 6.1.2) [de-facto estimand]. Missing data will be imputed using the NRI method (Section 6.3.1).

Additional analyses based on the ITT Population for Period 2 for ASAS40, include:

- Comparisons of each ixekizumab treatment group and placebo at postbaseline visits other than Weeks 16 and 52 using logistic regression analysis with treatment, geographic region, screening MRI/CRP status in the model (Section 6.1.2) [de-facto estimand]. Missing data will be imputed using the NRI method (Section 6.3.1).

- Comparisons of each ixekizumab treatment group and placebo at Weeks 16 and 52 and all other postbaseline visits using categorical MMRM analysis with treatment, geographic region, screening MRI/CRP status, visit, treatment-by-visit as fixed factors (Section 6.1.2) [de-jure estimand]. Data after initiation of biologic rescue of ixekizumab 80 mg Q2W will not be included in the categorical MMRM analyses.
- Comparisons of each ixekizumab treatment group and placebo at Weeks 16 and 52 and all other postbaseline visits using Fisher's exact test with NRI (Sections 6.1.2 and 6.3.1) [de-facto estimand]. Missing data will be imputed using the NRI method (Section 6.3.1).

Figures showing the proportion of patients achieving an ASAS40 response at each scheduled visit during Period 2 within each treatment group will be provided for ITT population and IR population.

Table RHBX.6.5 provides the detailed analyses including analysis type, method and imputation, population, time point, and treatment comparisons for the additional analyses on primary outcome.

#### **6.10.4. Other Secondary Efficacy Analyses**

There will be no adjustment for multiple comparisons for other secondary efficacy analyses.

The other secondary efficacy analyses include:

- ASAS40: analyses other than primary analysis (Section 6.10.1), and additional analysis of the primary outcome (Section 6.10.3)
- ASAS20, ASAS5/6 and partial remission
- Change from baseline in individual components of the ASAS criteria (patient global, spinal pain, function [see BASFI below], inflammation [see BASDAI below], CRP [see CRP below], and spinal mobility (lateral spinal flexion) [see BASMI below])
- Change from baseline in BASDAI: analyses other than major secondary efficacy analysis, 6 individual items and inflammation (mean of Q5 and Q6 on BASDAI)
- BASDAI 50
- Change from baseline in ASDAS: analyses other than major secondary efficacy analysis (Section 6.10.2)
- ASDAS inactive disease (ASDAS<1.3)
- ASDAS disease activity states: inactive disease, low disease activity, high disease activity, very high disease activity, clinically important improvement and major improvement
- Change from baseline in CRP
- Change from baseline in BASFI
- Change from baseline in mobility (BASMI linear and individual components, chest expansion, occiput to wall distance)
- Change from baseline in SPARCC SIJ score: analyses other than major secondary efficacy analysis (Section 6.10.2)
- Change from baseline in SPARCC SIJ structural score (SSS) for each of the 4 features: fat metaplasia, bone erosion, backfill and ankyloses.

- Change from baseline in enthesitis score (MASES and SPARCC)
- Change from baseline in TJC and SJC scores
- Incidence of peripheral arthritis by TJC and SJC scores of 46/44 joints.
- Incidence rate of anterior uveitis
- Change from baseline in ASAS-NSAID score, Section [6.10.4.1](#).

Treatment comparisons of each ixekizumab treatment group and placebo at Weeks 16 and 52 and all other postbaseline visits during Period 2 for the ITT Population will be provided. For inadequate responders who were treated with biologic rescue of ixekizumab 80 mg Q2W, only data up to the time of initiation of biologic rescue of ixekizumab 80 mg Q2W will be included in these analysis.

The impact of ixekizumab starting doses will be evaluated for the selected categorical responses and mean change in selected continuous efficacy and health outcome measures at Weeks 16 and 52 and earlier time point as described in Section [6.1.2](#).

Descriptive statistics (that is, no inferential testing) will be provided for each treatment group for the Inadequate Response Population during Period 2.

[Table RHBX.6.5](#) provides the detailed analyses including analysis type, method and imputation, population, time point, and treatment comparisons for other secondary outcomes.

#### **6.10.4.1. Analyses on NSAID Intake**

The ASAS-NSAID score is used to present the NSAID (including COX-2 inhibitor) intake by considering the type of NSAID, the total daily dose, and the number of days on which NSAID has been taken during a period of interest (Dougados et al. 2011). [Appendix 5](#) provides the equivalent dose of each NSAID compared to 150 mg diclofenac (Dougados et al. 2011), additional equivalent scores are listed below:

For the NSAID equivalent scoring system, 0 = no intake, 100 = 150 mg diclofenac, 1000 mg naproxen, 200 mg aceclofenac, 400 mg celecoxib, 600 mg etodolac, 90 mg etoricoxib, 200 mg flurbiprofen, 2400 mg ibuprofen, 150 mg indometacin, 200 mg ketoprofen, 15 mg meloxicam, 200 mg nimesulide, 400 mg phenylbutazone, 20 mg piroxicam, 20 mg tenoxicam (Dougados et al. 2011).

Additionally, 100 = 180 mg acetaminophen, 3600 mg acetylsalicylic acid, 3600 mg salicylic acid, 32 mg lornoxicam, 360 mg loxoprofen, 1000 mg mefenamic acid, 2000 mg nabumetone, 1000 mg niflumic acid, 600 mg tiaprofenic acid, 90 mg pelubiprofen, 240 mg zaltoprofen, 120 mg ketorolac tromethamine (if used intramuscularly [IM] or intravenous [IV]), 40 mg ketorolac, 400 mg sulindac, 1200 mg dexibuprofen, 75 mg deketoprofen, 1110 mg talniflumate. For Vimovo, esomeprazole strontium w/naproxen, esomeprazole w/naproxen and naproxen w/omeprazole, use the score for naproxen; for caffeine w/ibuprofen, CAROL-F, and famotidine w/ibuprofen, use the score for ibuprofen; for dioxaflex protect and arthrotec, use the score for diclofenac; for anacin /00141001, use the score for acetylsalicylic acid; for paynocil, use the score for salicylic acid.

The general formula for calculating ASAS-NSAID score is:

$$\frac{(\text{equivalent NSAID score}) \times (\text{days of intake during period of interest}) \times (\text{days per week})}{(\text{period of interest in days})}$$

A score is assigned depending on the frequency of NSAID use per week (Dougados et al. 2011):

- 7/7: everyday use
- 6/7: 6 days/week
- 4/7: 4 - 5 days/week
- 2/7: 2 -3 days/week
- 0.5/7: ≤1 day/week
- 0: no intake.

Using an example in Dougados and colleagues 2011, if during a period of interest (between 2 visits) of 6 months, the patient has taken piroxicam 20 mg during 4 months and if during this 4-month period he has taken piroxicam 3 to 5 days per week the calculation of ASAS-NSAID is as follows:

$$100 \text{ (20 mg piroxicam score)} \times 120 \text{ (4 months)} \times 4/7 \text{ (3-5 days/ week)} / 180 \text{ (6 months)} = 38.1$$

If the patient has used 10 mg piroxicam during the remaining 2 months on 2 days a week, the NSAID score for this period is:

$$50 \text{ (10 mg piroxicam score)} \times 60 \text{ (2 months)} \times 2/7 \text{ (1-3 days/week)} / 180 \text{ (6 months)} = 4.8$$

In this example, the total score for the 6-month period is 42.9 (38.1 plus 4.8).

The ASAS-NSAID score will be summarized for the following endpoints at baseline Week 0 (when applicable) and each scheduled visit of interest, which includes the timeframe after the date of previous visit to the date of current visit:

- Change from baseline in ASAS-NSAID
- Proportion of patients with 50% decrease in ASAS-NSAID scores compared with baseline
- Proportion of patients with ASAS-NSAID score <10
- Proportion of patients with ASAS-NSAID score = 0.

In addition, proportion of patients taking NSAID at specified visit will be summarized.

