For patients who experience a potential allergic/hypersensitivity reaction, consideration for any premedication for future injections will be agreed upon between the investigator and sponsor. Examples of potential allergic/hypersensitivity reactions that might merit premedication include mild-to-moderate skin rashes, mild-to-moderate generalized pruritus and/or urticaria, and mild-to-moderate injection site reactions (for example, injection site erythema, injection site pruritus, etc.). Patients who develop clinically significant systemic allergic/hypersensitivity reactions following administration of investigational product that do not respond to symptomatic medication or result in clinical sequelae or hospitalization are to be discontinued from study treatment and not receive further doses of investigational product, with or without premedication (see Section 7.1.1). Medications considered appropriate for premedication include, but are not restricted to, acetaminophen/paracetamol up to 1000 mg and antihistamines (for example, oral diphenhydramine 50 mg) given after all efficacy assessments have been completed for a given visit and 30 to 60 minutes prior to investigational product SC injection for visits where injections are administered at the clinic. For all other injections, patients may self-premedicate at home prior to administration of investigational product, as directed by the investigator. All such premedications will be recorded as concomitant medications. Corticosteroids are not permitted as agents for premedication.

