### *NSAIDs and Analgesics:*

NSAIDs, including COX-2 inhibitors, will be allowed up to the maximum recommended doses for pain. Patients must be on a stable dose of NSAIDs/COX-2 inhibitors for at least 2 weeks prior to baseline randomization. Introduction of a new NSAID or dose adjustment to an existing NSAID is not permitted, unless required for safety reasons (AE).

Short-acting analgesics with no anti-inflammatory action (such as paracetamol) are permitted. If administered ad hoc as needed, they are to be withheld within the 24-hour period prior to any

assessment. Aspirin (in a dose not exceeding 350 mg/day) may be taken to manage cardiovascular risk.

Opiate analgesic use is allowed but is not to exceed an average daily dose of 30 mg/day of morphine or its equivalent. Introduction of a new opiate analgesic or dose adjustment to an existing opiate analgesic is not permitted, unless required for safety reasons or as premedication for MRIs.

*Conventional DMARDs:*

Discontinuation of excluded oral or injectable cDMARDs before study enrollment must occur at least 4 weeks prior to baseline. MTX (oral or parenteral up to 25 mg/week), sulfasalazine (up to 3 g/day), or hydroxychloroquine (up to 400 mg/day) may be allowed IF at stable dose for at least 4 weeks prior to baseline randomization. These agents can only be used as single agent therapy and not in combination with other cDMARDs. If, at any time, the investigator believes that side effects or laboratory abnormalities may be attributable to the cDMARD, then cDMARD dose is to be lowered or the medication stopped. Local standard of care is to be followed for concomitant administration of folic or folinic acid if MTX is taken.

*Corticosteroids:*

*Oral corticosteroids:* If on oral corticosteroids, the dose must not exceed 10 mg/day of prednisone or its equivalent and must be stable for at least 4 weeks prior to baseline randomization. Treatment alteration in oral corticosteroid dose is not to occur prior to Week 16.

*Parenteral corticosteroids (intravenous, intramuscular, intra-articular):* Treatment with any parenteral corticosteroids is not permitted within 6 weeks prior to baseline or up to Week 16.

*Inhaled and topical steroids:* Regular use of inhaled or topical steroids will be permitted during any study period.

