#### **8.1.2.13. NSAID Intake**

Information regarding NSAIDs intake will be collected in the eCRF, and the ASAS-NSAID score will be calculated at baseline and through Week 52 (Dougados et al. 2011).

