### 3. Revision History

Statistical analysis plan (SAP) Version 1 was approved prior to first permanent data transfer, on 09 November 2016.

#### Revisions since Version 1

Section	Revision
Entire document	Editorial changes on minor grammatical or formatting changes as needed
Section 4 Objectives	Updated primary objective per protocol amendment (b); In addition, made the following changes to major secondary objectives: 1. Replaced BASFI with SF-36 PCS 2. Changed ASDAS inactive disease to ASDAS low disease activity; 3. Removed objective for Changed clinically meaningful changes in background therapy due to sparse data 4. Added BASDAI change from baseline  Added starting dose analyses for additional endpoints for secondary objective
Section 5.2 Determination of Sample Size	Updated per protocol amendment (b)
Section 5.3 Method of Assignment to Treatment	Clarified stratification factor
Section 6.1.1 Analysis Populations	Clarified the PPS population Table 6.1 – add additional continuous efficacy and health outcome analyses for IR population besides the categorical efficacy analyses
Section 6.1.2 General Considerations for Analyses during the Blinded Treatment Dosing Period (Period 2)	Removed the time-to response analysis
Section 6.1.2.2.	Clarified the treatment period for the biologic IXE rescue
Section 6.3.2 Modified Baseline Observation Carried Forward	Clarified the mBOCF analysis for ITT population and IR population.
Section 6.3.3 Last Observation Carried Forward	Removed the LOCF analysis
Section 6.3.4 and Section 6.3.5	Clarified pMI and tipping point analysis
Section 6.5 Multiple Comparisons /Multiplicity	Updated multiplicity scheme per protocol amendment and update to major secondary objectives
Section 6.7 Patient Characteristics	Updated/clarified some baseline variables
Section 6.7.2 Historical Illness and Preexisting Conditions	Updated analyses for pre-existing conditions for Period 2
Section 6.9.1 Previous Therapy	Removed Previous therapy due to redundancy to previous AxSpA therapy
Section 6.9.2 Concomitant therapy	Removed analysis for premedication for allergic reaction
Section 6.10 Efficacy analyses Table 6.4 and Table 6.5	Updated the analyses for TJC/SJC, ethesitis and anterior uveitis and MRI scores
Section 6.10.4.1 Analyses on NSAID Intake	Added NSAID equivalent scoring system from reference and from medical input

Section	Revision

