		Proportion of patients with SJC = 0 for patients with current or historical peripheral arthritis at Baseline	Analysis of SJC = 0 only applies to patients with current or historical peripheral arthritis at Baseline	Missing if observed value is missing

Measure	Description	Variable	Derivation / Comment	Imputation Approach if with Missing Components
Anterior Uveitis	At each study visit, study health care providers will evaluate the patient for any symptoms of anterior uveitis.	Incidence and incidence rate of anterior uveitis	Anterior uveitis will be summarized for patients with or without prior anterior uveitis, separately.  Anterior uveitis is identified using the preferred term “iridocyclitis”.	Not applicable (NA)
Non-Steroidal Anti-Inflammatory Drug (NSAID) Intake	Information regarding NSAIDs (including COX-2 inhibitors) intake will be collected in the eCRF and the ASAS-NSAID score will be calculated (Dougados et al. 2011).	Proportion of patients taking NSAID	Proportion of patients taking NSAID (including COX-2 inhibitor) at specified visit	NA
		ASAS - NSAID score	See Section 6.10.4.1 and Appendix 5 for details of deriving ASAS-NSAID score. ASAS-NSAID = 0 if no NSAID use	If NSAID dose is missing, the maximum efficacy dose (Appendix 5) is assumed. If frequency is missing, ‘every day’ intake is assumed. If start/stop dates are missing, follow missing date rule in Section 6.9.2
		ASAS-NSAID score change from baseline	Calculated as: observed ASAS-NSAID score – baseline ASAS-NSAID score	
		ASAS-NSAID50	$100 \times \frac{\text{Baseline ASAS} - \text{NSAID} - \text{Observed ASAS} - \text{NSAID}}{\text{Baseline ASAS} - \text{NSAID}}$ Proportion of patients with at least 50% decrease from baseline in ASAS-NSAID score. Derivation only applies to patients whose ASAS-NSAID is not equal to 0 at baseline.	

Measure	Description	Variable	Derivation / Comment	Imputation Approach if with Missing Components
MRI Sacroiliac Joint (SIJ) (Spondyloarthritis Research Consortium of Canada [SPARCC] Score)	Both left and right SIJ are scored for bone marrow edema. Each side has 6 slices and each slice has 6 scoring units, score of 0 or 1. Total SIJ SPARCC scores can range from 0 to 72 with higher scores reflecting worse disease. Scoring will be performed by a central reader.	SPARCC SIJ Score	The SPARCC SIJ Score is sum of 72 scoring units; the sum ranges from 0 to 72.	See “MRI Data Programming Guidance for AxSpA Studies’ for missing rule and imputation method.

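### SAP 6.10.4.1 scores 180 mg acetaminophen as a full NSAID dose, against the score's own definition, its zero rule and the protocol's description of paracetamol

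*SAP*

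**What the plan says.** SAP 6.10.4.1 opens with the purpose of the score: "The ASAS-NSAID score is used to present the NSAID (including COX-2 inhibitor) intake". It assigns 100 to 150 mg diclofenac and to listed doses of other NSAIDs taken from a published recommendation, then adds a second set of equivalents that begins "Additionally, 100 = 180 mg acetaminophen, 3600 mg acetylsalicylic acid, 3600 mg salicylic acid". The SAP revision history gives the origin of the list only as "Added NSAID equivalent scoring system from reference and from medical input".

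SAP Table RHBX.6.4 adds the rule "ASAS-NSAID = 0 if no NSAID use".

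The protocol's concomitant-medication rules, in 6.8.1 (Weeks 0 to 16) and again in 6.8.2 (Week 16 onward), say "Short-acting analgesics with no anti-inflammatory action (such as paracetamol) are permitted". Protocol 6.6.1 shows that the two names mean one drug: in its premedication rule it refers to "acetaminophen/paracetamol up to 1000 mg and antihistamines".

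The outputs built on the score are change from baseline, at least a 50% decrease (ASAS-NSAID50), the proportion below 10 and the proportion equal to 0 (SAP 6.10.4.1 and Table RHBX.6.4). The baseline score is also a baseline characteristic (SAP 6.7.1).

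**The concern.** Take a patient who uses acetaminophen and no NSAID. If acetaminophen is not an NSAID, as the protocol's wording indicates, the rule in Table RHBX.6.4 gives 0. The list in 6.10.4.1 gives a positive score. Two parts of the same plan then return different values for the same patient.

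The size of the entry adds to the doubt. The only acetaminophen dose the documents mention elsewhere is the 1000 mg premedication maximum, and under the list that amount is worth more than five times the diclofenac reference.

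At stake is whether the NSAID-intake summaries, a named other-secondary endpoint, measure NSAID use or partly measure use of a simple analgesic.

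**Working it through.** **Inputs**
- Score 100 = 180 mg acetaminophen; score 100 = 150 mg diclofenac; formula; lowest non-zero frequency weight 0.5/7 for use on at most 1 day per week (SAP 6.10.4.1).
- Thresholds below 10 and equal to 0 (SAP 6.10.4.1); zero rule and ASAS-NSAID50 (SAP Table RHBX.6.4).
- 1000 mg: premedication maximum in protocol 6.6.1. 500 mg, and all frequencies and durations below, are my assumptions.
- 28 days: the spacing of, for example, Weeks 16 and 20 in the Schedule of Activities.

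**Formula:** score = equivalent score × days of intake × weekly weight ÷ days in period. Dose scales linearly, as in the SAP's example, where half the piroxicam dose scores 50.

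**The SAP's own example reproduces:**
- 100 × 120 × (4/7) ÷ 180 = 38.1
- 50 × 60 × (2/7) ÷ 180 = 4.8
- Sum = 42.9, as stated.

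**Equivalent score of acetaminophen under the list:**
- 1000 mg: 100 × 1000 ÷ 180 = 555.6
- 500 mg: 100 × 500 ÷ 180 = 277.8

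**Amount added for a patient on no NSAID, weight 0.5/7** (expected value under the zero rule: 0)

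| Dose | Intake | Added score | Below 10? | Equal to 0? |
|---|---|---|---|---|
| 1000 mg | whole period | 555.6 × 0.5/7 = 39.7 | fails | fails |
| 500 mg | whole period | 277.8 × 0.5/7 = 19.8 | fails | fails |
| 1000 mg | 7 of 28 days | 39.7 × 7/28 = 9.9 | passes | fails |
| 1000 mg | 1 of 28 days | 39.7 × 1/28 = 1.4 | passes | fails |

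With intake over the whole period, the dose that reaches 10 at this weight is 10 × 180/100 × 14 = 252 mg. The below-10 result therefore depends on duration; the equal-to-0 result does not.

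**Change from baseline.** Table RHBX.6.5 restricts change and ASAS-NSAID50 to patients with NSAID intake at baseline. Within that group, a spurious 39.7 shifts the change by +39.7 if it occurs only at follow-up, by −39.7 if only at baseline, and by 39.7 − 39.7 = 0 if at both.

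**ASAS-NSAID50.** Suppose a patient stops 150 mg daily diclofenac and takes 1000 mg acetaminophen daily throughout. The score goes from 100 + 555.6 = 655.6 to 555.6, a decrease of 100 ÷ 655.6 = 15.3%. Without the entry it goes from 100 to 0, a decrease of 100%. A complete NSAID stopper would be counted as not reaching 50%.

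**The case against.** The strongest reply is that the entry may never be used. The Schedule of Activities has a row for NSAID use separate from concomitant medications. Protocol 8.1.2.13 ties the score to NSAID data: "Information regarding NSAIDs intake will be collected in the eCRF, and the ASAS-NSAID score will be calculated at baseline and through Week 52". For premedication, protocol 6.6.1 says "All such premedications will be recorded as concomitant medications". SAP 6.7.1 and 6.15.1 treat baseline analgesic use as its own category. Appendices 5 and 12, which hold the dose equivalents and the medication definitions, are blacked out in the public copy, so it cannot be seen whether acetaminophen is screened out earlier. All of this stands, and it leaves the number of affected patients open, possibly at zero. It does not explain why a non-NSAID analgesic sits in an NSAID scoring list.

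It can also be said that the zero rule does not mention acetaminophen, and that the protocol's wording is a permission rule rather than a scoring definition. That is fair. The conflict comes from reading the three places together, and a deliberate choice through medical input cannot be excluded.

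A reader might infer three stronger things, and the documents support none of them.
- **That any occasional use breaks the below-10 summary.** The table above shows one day and seven days in 28 both passing at the lowest weight.
- **That the change-from-baseline results are biased in a known direction.** The shift can be positive, negative or zero, and applies only to patients counted as having NSAID intake at baseline.
- **That only descriptive output is involved, or conversely that efficacy conclusions are at risk.** Table RHBX.6.5 calls these analyses descriptive, but SAP 6.10.4 lists the change in score among outcomes for which treatment comparisons are provided, and 6.7.1 compares continuous baseline characteristics by ANOVA. None of these is a primary or major secondary test.

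**Conclusion.** The inconsistency is real and minor. As written, the scoring list gives a positive NSAID score to a drug that the protocol describes as having no anti-inflammatory action, within a score defined as NSAID intake and set to zero without it. Nothing visible corrects the entry.

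The effect is conditional on acetaminophen records reaching the lookup. If they do, a patient on no NSAID wrongly fails the equal-to-0 summary at any dose, and wrongly fails the below-10 summary when intake is long enough. Exposure is confined to ASAS-NSAID outputs: the other-secondary intake summaries and the baseline comparison. ASAS40, the major secondary endpoints and the alpha allocation are untouched.

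Confidence is high that the entry is present and conflicts with the other text, and low on whether it has any numerical effect. The documents do not show whether the drug name, the dose or neither was the slip.

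**What to change.** Check both the drug name and the 180 mg figure against the reference and the medical input from which the added equivalents were taken. Then take one of three routes:
- If another drug was meant, correct the name and the dose.
- If there is no basis for scoring acetaminophen, remove it from the list in SAP 6.10.4.1 and from the programmed lookup, so that non-NSAID analgesics contribute 0.
- If inclusion was deliberate, state the reason, confirm the dose, and align the definition in 6.10.4.1 with the zero rule in Table RHBX.6.4.

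The cost is one source check, one list entry and one lookup entry; the third route also needs a sentence or two in the SAP. No change to data collection or to any tested hypothesis is needed.
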